## JHM IRB - eForm A – Protocol

- Use the section headings to write the JHM IRB eForm A, inserting the appropriate material in each. If a section is not applicable, leave heading in and insert N/A.
- When submitting JHM IRB eForm A (new or revised), enter the date submitted to the field at the top of JHM IRB eForm A.

\*\*\*\*\*

### 1. Abstract

With potent analgesic properties, perceived hemodynamic benefits and limited alternatives, opiates are the analgesic mainstay for acute coronary syndrome (ACS) patients reporting peri-procedural pain or nitrate-resistant chest pain. However, large observational studies suggest that opiate administration during ACS may result in adverse cardiovascular outcomes. Complimenting this, a number of recent mechanistic studies have demonstrated delayed and attenuated effects of oral dual anti-platelet therapy (DAPT) on platelet inhibition endpoints among subjects receiving intravenous morphine. These studies support the hypothesis that morphine delays the gastrointestinal absorption of DAPT medications. However, no data exist on the impact of intravenous fentanyl, a systemic opioid analgesic routinely administered during percutaneous coronary intervention (PCI) procedures, on the platelet inhibition effects of DAPT. We hypothesize that, similar to morphine, fentanyl administered at the time of PCI will reduce and delay the effect of DAPT on platelet function. As such, the primary aim of this study is to test the impact of intravenous fentanyl on residual platelet reactivity by randomizing patients undergoing PCI to a strategy of peri-procedural benzodiazepine plus non-systemic local analgesia or to the current standard of benzodiazepine plus intravenous fentanyl. Our study will address a major gap in knowledge. PCI analgesia with fentanyl is often administered concurrently with loading doses of DAPT, particularly in ACS. Given the critical need for rapid and robust inhibition of platelet function during PCI, our research study has true potential to change clinical practice, particularly if we demonstrate reduced DAPT absorption and elevated residual platelet reactivity among patients receiving fentanyl during PCI. As such, this research could result in a paradigm shift in the analgesia management of PCI and have a profound impact on optimization of post-PCI cardiac outcomes.

### 2. Objectives

**Primary Objective:** We will test the hypothesis that randomization to fentanyl will be associated with higher residual platelet reactivity, as determined by mean P2Y12 reactivity units (PRUs) at 2 hours, among persons undergoing PCI with IV fentanyl analgesia (as well as aspirin and ticagrelor), compared to subjects randomized to undergo PCI with non-systemic analgesia.

**Secondary Objective:** To test the hypothesis that fentanyl administered during PCI will adversely impact the pharmacokinetics of ticagrelor, as determined by the area under the curve of active metabolite measured using liquid chromatography tandem mass spectrometry.

[figure not shown]
**Secondary Objective:** To test for differences in patient reported pain scores and biomarkers of myocardial injury, comparing PCI patients randomized to peri-procedural benzodiazepine plus non-systemic local analgesia or to the current standard of benzodiazepine plus intravenous fentanyl.

### 3. Background

[figure not shown]
Morphine has long played a central role in the management of ACS. However, a 2005 observational study suggested that patients receiving morphine for pain relief in ACS had worse outcomes. In this context, recent research demonstrates that intravenous morphine delays and inhibits the absorption of oral DAPT with resultant delay in the time to maximal platelet inhibition. Hobl *et al.* administered a loading dose of 600mg clopidogrel together with either placebo or 5mg morphine intravenously in a randomized, double-blind, cross-over mechanistic trial. Morphine injection delayed clopidogrel absorption ( $T_{max}$ : 105 vs. 83 min,  $p = 0.025$ ) and reduced the total exposure to its active metabolite by 34% ( $p = 0.001$ , **figure 1**). Morphine also resulted in higher residual platelet aggregation and delayed maximal inhibition of platelets by 2 hours ( $n = 24$ ;  $p < 0.001$ ). Similar results have recently been reported for subjects receiving ticagrelor. Morphine's association with emesis, inhibition of gastric emptying and reduced GI motility is hypothesised as the cause.

Delayed and reduced absorption of DAPT in ACS patients is likely to translate into worse cardiovascular outcomes because maximal inhibition of platelet function is necessary to treat intracoronary atherosclerotic plaque rupture and thrombosis, as well as to minimize the risk of in-stent thrombosis among patients who receive coronary stents at the time of PCI. In keeping with this, morphine has also recently been associated with suboptimal reperfusion after PCI in patients with ACS (**figure 2**). As a consequence, 2015 European guidelines now state, “*in ACS patients whose ischemic symptoms are not relieved by nitrates and beta-blockers, opiate administration is reasonable..., with the caveat that morphine may slow intestinal absorption of oral platelet inhibitors.*”

However, no data exist as to the impact of **fentanyl**, another IV opiate, on DAPT absorption and platelet inhibition. This represents a major gap in current knowledge. Indeed, fentanyl is used for analgesia in the vast majority of PCI procedures in Europe and the US, often being administered concurrently with loading doses of DAPT. It is known that fentanyl has similar effects to morphine on GI motility and that the typical fentanyl PCI dose, 25-50mcg, is equipotent with the morphine dose used by Hobl and Kubica in two recent trials (5mg). Given the critical need for rapid and robust inhibition of platelet function among patients receiving intracoronary stents during PCI, this research proposal has true potential to change clinical practice, particularly if our results confirm reduced DAPT absorption and elevated residual platelet reactivity among patients receiving fentanyl during PCI. As such, this research could result in a paradigm shift in the analgesia management of PCI and have a profound impact on optimization of post-PCI clinical outcomes.

**Figure 1- Morphine Lowers Plasma Concentrations of Clopidogrel Active Metabolite.** \*\* $p \leq 0.01$  JACC 2014;63:630-5

**Figure 2- Morphine adversely impacts post PCI infarct size & myocardial salvage index by MRI.** Clin Res Card 2015;104:727-34

[figure not shown]
#### 4. Study Procedures

##### a. Study design, including the sequence and timing of study procedures

This is an open-label randomized controlled trial. We will accrue 70 patients undergoing loading of oral DAPT (aspirin and ticagrelor 180mg [the latter only being administered if a stent procedure is necessary]) as part of routine clinical care. This may require that up to 300 patients will need to be approached for consent. The reason for this is that only about 1 in 4 patients who undergo left heart catheterization actually need DAPT loading for stent placement (many do not need stents) and it is impossible to know who these patients will be before the catheterization procedure is performed.

Consenting patients will be randomized, 1:1, to peri-procedural intravenous benzodiazepine plus non-systemic local analgesia or to the current standard of peri-procedural intravenous benzodiazepine plus intravenous fentanyl plus local analgesia (**figure**).

Peri-procedural analgesia is part of routine clinical care, thus, the primary research procedure in this study is the randomization to the type of analgesia (fentanyl vs. no fentanyl).

Subsequent to randomization, clinical care will then proceed as per normal practice (e.g. patients requiring coronary stenting will undergo the procedure at the discretion of the interventional cardiologist). However, because ticagrelor is a newer DAPT option and is less commonly given at our hospital than clopidogrel, we will require that patients enrolled into our study not be switched from ticagrelor to clopidogrel within the first 12 hours of the initial ticagrelor load in the catheterization lab (this is due to theoretical concerns that clopidogrel loading is less effective

within the first 12 hours of ticagrelor loading due to competition for platelet receptors). As such, we require all patients enrolled into the study to be admitted for observation for 12-24 hours after enrolment. Ticagrelor was chosen for this study as it is a potent and fast-acting agent, has been demonstrated to be superior to clopidogrel, and will allow us to answer the main research question as to whether, or not, fentanyl delays the GI absorption of oral anti-platelet agents.

In order to address our research objectives, enrolled patients will need to undergo sampling of blood after randomization (**figure**). While such blood sampling is typical in routine clinical care, we will also be obtaining blood for the sole purposes of research. Blood will be sampled at 0, 0.5, 1, 2, 4, and 24 hours after randomization. Where possible, blood will be drawn from existing IV access. For research purposes, we will also obtain patient-reported procedural pain data using the visual analog scale and the numeric rating scale at 2 hours (NRS).

*b. Study duration and number of study visits required of research participants.*

The duration of the study will be over 24 hours. The only study visit required is the admission during which the PCI is being performed as part of routine clinical care. Of note, patients undergoing PCI are routinely kept in the hospital for a minimal of 24 hours.

*c. Blinding, including justification for blinding or not blinding the trial, if applicable.*

Patients will not be blinded to the analgesia strategy (benzodiazepine sedation and local vs systemic analgesia) as the coronary angiogram is being performed as part of routine clinical care and it will not be possible to blind medical providers to the medications administered during the procedure. However, the collaborators who perform the analyses of blood samples will be blinded to the randomized allocation in order to minimize ascertainment bias.

*d. Justification of why participants will not receive routine care or will have current therapy stopped.*

All subjects enrolled will receive standard clinical care. The only change from standard practice is the 50% chance of being randomized to peri-procedural intravenous benzodiazepine plus non-systemic local analgesia. This will consist of benzodiazepine and local anaesthetic (e.g. subcutaneous lidocaine), as described below. We believe this is ethically justifiable for the following reasons; 1) the procedural pain is typically minimal, with the vast majority of patients undergoing radial approach to left heart cath; 2) benzodiazepine and local anesthetic are well known to provide effective comfort for patients who can't receive opiates (e.g. due to allergy); 3) those patients who complain of breakthrough pain in the non-systemic analgesia arm **are allowed receive bail-out IV opiates** in our research protocol; and 4) our hypothesis is that IV opiates may themselves be causing **indirect harm** in the setting of PCI by attenuating the effects of DAPT. Indeed- in the context of research demonstrating that morphine reduces and delays the effect of DAPT on platelet inhibition- our primary hypothesis is that the impact of intravenous fentanyl on platelet inhibition outcomes will be similar. However, because no studies have evaluated this question, there is a state of clinical equipoise. The only way to answer this pressing clinical question is to randomize patients to non-systemic analgesia, while ensuring patient discomfort is no different, and to compare platelet function results in these patients to a similar group of patients who are randomized to the current standard of peri-procedural intravenous benzodiazepine plus intravenous fentanyl.

e. *Justification for inclusion of a placebo or non-treatment group.*

There is no placebo or non-treatment group in this randomized trial.

f. *Definition of treatment failure or participant removal criteria.*

Treatment failure will be defined as subject-report of uncontrolled pain or discomfort during the PCI procedure. As part of routine care patients are regularly asked to report any pain during the procedure. In all instances, and most notably in the group randomized to initial intravenous benzodiazepine plus non-systemic analgesia, post randomization analgesia will be managed as per usual by the procedural team. Specifically, the study protocol only provides initial guidance on analgesia, based on the randomized allocation. Once the initial analgesia has been provided, should patients subsequently report uncontrolled pain or discomfort, the treating team can administer any analgesia that they feel is clinically indicated, including intravenous fentanyl in either arm of the study. There are no protocol-based removal criteria. However, participants can remove themselves at any time from the study as participation is voluntary.

g. *Description of what happens to participants receiving therapy when study ends or if a participant's participation in the study ends prematurely.*

When the study ends or should participation end prematurely, all subjects enrolled will undergo routine treatment as per usual best practice. Participants will be analyzed on an intention to treat basis. Therefore, participants will be analyzed based on their initial randomized analgesia allocation and whether or not their participation in the study ended prematurely.

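### Blood draws are timed from randomisation, but the ticagrelor load comes later, so the primary 2-hour PRU falls at a time since the dose that varies by patient

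*Combined protocol and SAP*

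**What the plan says.** - **Sampling clock (section 4a).** "Blood will be sampled at 0, 0.5, 1, 2, 4, and 24 hours after randomization".
- **Order of events (section 4a).** Patients consent and are randomised 1:1. Then "Subsequent to randomization, clinical care will then proceed as per normal practice". Ticagrelor is conditional on what the catheterisation shows: "the latter only being administered if a stent procedure is necessary". On which patients will need it, the section says "it is impossible to know who these patients will be before the catheterization procedure is performed". The switching rule in the same section locates the dose: "within the first 12 hours of the initial ticagrelor load in the catheterization lab".
- **Primary endpoint (sections 2 and 7a).** The objective is tested "as determined by mean P2Y12 reactivity units (PRUs) at 2 hours". Section 7a also says only 2 hours. Neither names the event from which the hours are counted.
- **Collection form (section 7b).** Hour 0 is headed as pre-procedure, hours 0.5 and 1 as intra-procedure, and hours 2, 4 and 24 as post-procedure. Each draw has a date and time field. There is no field for the time of the load.
- **Sample size (section 7c).** The control value is a 2-hour PRU of about 230 (SD 25) in patients given 180 mg ticagrelor, with a 20% increase assumed under fentanyl.

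**The concern.** Section 4a gives the main research question as whether fentanyl delays gastrointestinal absorption of oral antiplatelet agents. Time since the oral dose is the axis of that question. The only explicit time origin in the readable text is randomisation, which comes before the dose by an interval that the procedure determines.

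The nominal 2-hour PRU is then taken at a different time since the load in each patient, and always at less than 2 hours. The 2-hour light transmission aggregometry has the same fault. The ticagrelor AUC and the time-averaged PRU share the clock, and their early samples may fall before any drug has been given. The sample size in section 7c appears to rest on a PRU measured 2 hours after the load, which would be a different quantity from the one the plan collects.

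**Working it through.** **Step 1: the order of events.** Section 4a gives randomisation, then catheterisation, then the stent decision, then the load. So L, the time from randomisation to load, is greater than zero and depends on the procedure. No readable section sets L, limits it, gives a sampling window, or adjusts for time since the load. The form's hour 0 is pre-procedure, so hour 0 is not the load. The form does not say from what event the later draws are counted.

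**Step 2: time since the load.** Time since load = nominal time − L.

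- 0.5 h draw: at or before the load when L ≥ 30 min.
- 1 h draw: at or before the load when L ≥ 60 min.
- 2 h draw: at or before the load when L ≥ 120 min.
- The form schedules five pharmacokinetic draws (0.5, 1, 2, 4 and 24 h). The number after the load is 5 if L < 30 min, 4 if 30 ≤ L < 60 min, and 3 if 60 ≤ L < 120 min.

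Illustration for assumed values of L, which the documents do not give (hours since load):

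| L | 0.5 h draw | 1 h draw | 2 h draw | 4 h draw | 24 h draw |
|---|---|---|---|---|---|
| 15 min | 0.25 | 0.75 | 1.75 | 3.75 | 23.75 |
| 30 min | 0 | 0.5 | 1.5 | 3.5 | 23.5 |
| 45 min | −0.25 | 0.25 | 1.25 | 3.25 | 23.25 |
| 60 min | −0.5 | 0 | 1.0 | 3.0 | 23.0 |

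**Step 3: scale.** Section 3 reports two delays caused by morphine with clopidogrel: 105 − 83 = 22 minutes in the time to peak concentration, and 2 hours in maximal platelet inhibition. Neither is fentanyl with ticagrelor, so they serve only as context for the timing shifts above.

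**Step 4: power.** The planned difference is 0.20 × 230 = 46 PRU with SD 25.

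- *The plan's own figure.* A two-sided t-test at 0.05 with 90% power needs 7.3, so 8, per group. Section 7c states at most 23, which is true as a bound but is not what these inputs produce. A figure of 23 would need an SD near 47. The timing point does not depend on this.
- *Headroom.* With 35 per arm (70 ÷ 2), power stays at 90% or more until the SD reaches 58.5 at a difference of 46 PRU, or until the difference falls to 19.7 PRU at SD 25, which is 1 − 19.7/46 = 57% smaller. With 30 per arm, as an example of drop-out, the limits are SD 54.0 and 21.3 PRU.

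The documents give neither L nor the rate at which PRU falls after the load, so they cannot say whether variable timing would reach these limits.

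**The case against.** The strongest reply is that no harm to the comparison is shown. Randomisation is a valid common origin for comparing two strategies by intention to treat. A delay unrelated to arm leaves the type I error intact, and on the plan's own inputs there is ample spare power. That stands, and it limits the severity. It does not make the 2-hour value a 2-hour post-dose value. Nor is L guaranteed to be the same in both arms, since section 4c leaves treating staff unblinded.

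Other points have partial force:

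- **Load time.** The rule in sections 4a and 8a against switching within 12 hours of the load implies that its time will be known clinically, and the form may not be the whole case report form. But the plan gives that time no role in sampling or analysis.
- **AUC and mixed models.** Draw times are recorded, so with the load time both could be analysed on actual time since dose. This would not restore early post-dose samples that were drawn before the load, and it would not repair the fixed 2-hour PRU and aggregometry.
- **Section 7c.** Reading its 2-hour PRU as time since the load is an inference. The mismatch with the sample size is therefore a secondary argument.
- **Design figure.** It cannot be read here and may show a load-based timeline. If so, the text of section 4a contradicts it and the two must be reconciled.
- **Hospital stay.** A 24-hour draw already exceeds the lower end of the 12-24 hour stay in section 4a, whatever the anchor.

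**Conclusion.** The concern holds and should be fixed. Followed exactly, the plan takes its primary measurement 2 h minus L after the ticagrelor load, with L unspecified and free to vary by patient. The size of the timing shift is L itself: 15 to 60 minutes under the illustrative assumption, which puts the primary sample 1.75 to 1.0 h after the dose. The loss of early post-dose draws at L of 30 and 60 minutes follows from arithmetic alone. The effect on PRU cannot be computed from the documents.

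The harm shown is to what the endpoint means. Bias between arms and loss of power are not shown. The conclusion rests on the readable text, in which randomisation is the only stated origin for the draws.

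**What to change.** 1. Define time zero for the PRU, aggregometry and pharmacokinetic draws as administration of the ticagrelor load. Keep the pre-procedure draw as baseline and count the 0.5, 1, 2, 4 and 24 h draws from the load.
2. Restate the primary outcome as PRU 2 hours after the ticagrelor load.
3. Add three clock times to the collection form: randomisation, first fentanyl dose and ticagrelor load.
4. State that the AUC and the mixed models use actual time since the load.
5. Give the anchors for troponin and for the 2-hour pain score separately. Section 7b collects pain in all 300 consented patients, including those who never receive a load.
6. Make sections 2, 4a, 7a, 7b, 7c and the design figure agree.

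**Cost.** Changes to wording and three time fields, with the same number of draws and no extra patients. The last draw moves to 24 h + L after randomisation, which is 24.25 to 25.0 h for the assumed 15 to 60 minutes. This must be checked against the planned stay, on which the protocol is itself not uniform. Section 4a says "we require all patients enrolled into the study to be admitted for observation for 12-24 hours after enrolment", while section 4b says "patients undergoing PCI are routinely kept in the hospital for a minimal of 24 hours".

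### Does the intention-to-treat sentence leave the primary PRU analysis set in doubt, when only about one in four randomized patients receives ticagrelor?

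*Combined protocol and SAP*

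**What the plan says.** Section 4g states "Participants will be analyzed on an intention to treat basis" and goes on to explain that "participants will be analyzed based on their initial randomized analgesia allocation", whether or not their participation ended early. Section 4f gives no criteria for removing patients.

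Section 4a sets the order of events. Consenting patients are randomized 1:1. Then "Subsequent to randomization, clinical care will then proceed as per normal practice", and "patients requiring coronary stenting will undergo the procedure at the discretion of the interventional cardiologist". Ticagrelor is conditional, "the latter only being administered if a stent procedure is necessary". The plan expects that "only about 1 in 4 patients who undergo left heart catheterization actually need DAPT loading for stent placement" and adds that "it is impossible to know who these patients will be before the catheterization procedure is performed". The target is nevertheless stated in loaded patients: "We will accrue 70 patients undergoing loading of oral DAPT".

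Section 7a makes mean PRU at 2 hours the primary outcome, measured in both randomized groups, without naming a population. Section 7b compares pain in all 300 consented patients. Section 7c bases the sample size on patients who received ticagrelor.

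**The concern.** Taken alone, the sentence in Section 4g covers everyone randomized. Most of those patients never receive the drug whose absorption is under study. A literal all-randomized analysis of PRU would average the effect of interest with patients who cannot show it, and so would not answer the primary objective in Section 2.

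The alternative is to analyze only loaded patients. That answers the objective, but the set is formed after randomization, by operators who know the allocation (Section 4c). It is not intention to treat in the full sense, and readers told that it is might not ask whether loading differed by arm. If the choice of set were truly open, it could also be made after the data were seen.

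**Working it through.** **The plan's own figures.** Section 7c gives a control mean of about 230 PRU, SD 25, a 20% increase, two-sided alpha 0.05 and 90% power.
- Planned difference: 0.20 × 230 = 46 PRU.
- n per group = 2 × (1.960 + 1.282)² × 25² / 46² = 6.2, so 7 (8 with the exact t-test). The stated figure of at most 23 therefore holds only as an upper bound. That is a separate matter, and nothing below depends on it.
- Loading rate: 70/300 = 23.3%, and 70/0.25 = 280. The figures of one in four, 300 and 70 agree with one another.

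**Which set the plan points to for PRU.**
- Section 2: the primary hypothesis concerns patients undergoing PCI who also receive aspirin and ticagrelor.
- Sections 4a and 7c: the target is 70 loaded patients, and the mean and SD are for ticagrelor recipients.
- Section 7b: all 300 are named for pain only, and a ticagrelor metabolite area under the curve has no meaning without ticagrelor.
- Section 4a: the ticagrelor switching rule and the observation stay attach to enrolled patients, as does the research blood sampling. This suggests that enrolment there means loading. Section 4d uses the word more loosely, so this is support and not proof.
- Section 4g: the explanatory sentence concerns grouping by allocation and early end of participation, under a heading about premature end. It follows Section 4f, which allows fentanyl later in either arm. It tells the analyst not to regroup crossovers or drop early leavers.

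All of these are consistent with one analysis: randomized patients who were loaded, compared by allocated arm.

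**Power of that analysis.** With 35 per arm, the standard error is 25 × √(2/35) = 5.98 and 46/5.98 = 7.7. Power exceeds 99.9%.

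**What the literal reading would give.** Assume no fentanyl effect on PRU without ticagrelor. The difference becomes 0.25 × 46 = 11.5 PRU, or 0.233 × 46 = 10.7 PRU.

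Power also depends on the gap g between the mean PRU of unloaded patients and that of loaded controls. The documents do not give g, so it is assumed here. With p the share loaded, the variance is 25² + p(1−p)g² in the control arm and 25² + p(1−p)(g−46)² in the fentanyl arm, averaged over arms. Section 5 excludes P2Y12 inhibitors within 14 days and Section 4a describes ticagrelor as potent, so only gaps of zero or more are shown. With 150 per arm:

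| Gap g (PRU, assumed) | SD, p = 0.25 | Power, p = 0.25 | Power, p = 70/300 |
|---|---|---|---|
| 0 | 28.7 | 93% | 90% |
| 50 | 29.3 | 92% | 89% |
| 100 | 42.8 | 64% | 60% |

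The main fault of the literal reading would be the wrong question. Loss of power is serious only if the gap is large. Either way, this is the cost of an analysis that the plan does not lead to.

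**What a loading-rate comparison could show.** At 25% loading and 150 per arm, the 95% confidence interval for the difference has half-width 1.96 × √(2 × 0.25 × 0.75/150) = 0.098, about 10 percentage points. A similar rate in both arms would not show that selection is absent.

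**The case for a change.** The strongest case for a change is that the only explicit analysis rule says intention to treat, while the primary set has to be inferred from the objective and the accrual wording. Operators are unblinded, stenting is at their discretion, and no report of loading by arm is planned. A prespecified plan should name its primary set, and doing so costs a sentence and a table. Section 5 adds to the unease by requiring PCI, although Section 4a says the need is unknown before catheterization. Sections 4a and 7b also differ on whether the 300 are approached or consented.

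Part of this stands. The loaded set is strictly a modified intention-to-treat set, and the label is loose. The plan does not say which set troponin uses. Loading counts and missing 2-hour values by arm belong in any report of the trial.

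None of it changes the primary comparison. The inference rests on several sections that agree, and grouping by allocation is stated outright. If the stent decision follows the angiographic findings, the comparison by arm should carry little bias, and no passage suggests that the analgesic allocation influences that decision. The proposed table would be too imprecise to settle the matter. The remaining differences in wording are clerical.

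**Conclusion.** No change to the plan is needed. Read as a whole, it already leads to a comparison by allocated arm of the roughly 70 loaded patients, with pain compared in all 300. A new label would leave that result untouched. This is a gap that analysts would fill sensibly, and filling it in the text brings no gain in the analysis.

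The fall from 46 to about 11 PRU applies only to the literal all-randomized reading, and only if fentanyl has no PRU effect without ticagrelor. The power figures for that reading rest further on assumed gaps.

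The conclusion rests on the stent decision not depending on the analgesic arm. The documents do not test this and give no sign against it. The design figure mentioned in Section 4a is not shown in the available text, so patient flow was taken from the written description.
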